8.1 PATIENT REGISTRATION AND DOCUMENTATION

8.2 STUDY PROTOCOL

9. STATISTICAL CONSIDERATIONS

9.1 STATISTICAL ANALYSIS 26

Steering Committee

Principal Investigator: [name] [name]
Professor of Medicine
Division of Gastroenterology and Hepatology
Mayo Clinic
[contact]

Coinvestigators: [name]
Division of Gastroenterology and Hepatology
Mayo Clinic
[contact]

[name].
Division of Gastroenterology and Hepatology
Mayo Clinic
[contact]

[name].
Division of Gastroenterology and Hepatology
Mayo Clinic
[contact]

[name].
Research Fellow
Division of Gastroenterology and Hepatology
Mayo Clinic

[contact]

Biostatistician

[name] Ph.D.

Biostatistics Unit

Mayo Clinic

[contact]

Pathologist:

[name] M.D.

Department of Pathology

Mayo Clinic

[contact]

Protocol Synopsis

Title of Study	Endoscopic ultrasound guided core biopsy needle versus fine needle aspiration (FNA) needle in tissue sampling of pancreas cancer for whole exome sequencing and genomic profiling: a prospective randomized controlled trial.
Hypothesis	Flexible core biopsy needles are more capable than fine needle aspiration in acquisition of tumor tissue that is important for pathological evaluation and genomic analysis. This would specifically allow us to perform whole exome sequencing of a tumor tissue and could provide path for future individualized pancreas cancer treatment. Thus, we hypothesized that FNB is superior to FNA in acquiring tumor tissue from pancreas mass that is key for genomic profiling.
Specific Aims	To compare FNB versus conventional FNA for whole exome sequencing and genomic profiling in tissue sampling of pancreas cancer. 
1. Per needle adequacy for un-amplified whole exome sequencing2. Per needle quantity of DNA.3. Per needle adequacy for cytology4. Per needle adequacy for histology5. Adverse events
Study design	Prospective, single blinded, randomized controlled trial of FNB versus FNA for whole exome sequencing and genomic profiling.

Sample size	50cases
Inclusion criteria	
 ▪ Male and female patients who are 18 years old or older and are referred for the evaluation of pancreatic mass lesion ▪ International Normalized Ratio (INR) less than 1.5 and platelet count of more than 50,000. ▪ Medically stable to undergo sedation for EUS. ▪ Signed informed consent
Exclusion criteria	
 ▪ Medical condition that preclude the patient from having a therapeutic procedure regardless of the EUS finding ▪ Pregnant patients
Study design	
This is a prospective, single blinded randomized controlled trial with a paired evaluation of FNB vs FNA for whole exome sequencing and genomic profiling. A minimum 2 passes (1 with each needle) will be performed from form pancreas stratified by the lesion location (pancreas head tumor vs pancreas body/tail). Based on the location and type of the abnormal lesion, if further investigation via FNA is deemed necessary by the participating endosonographer, conventional FNA will be alternated with FNB in the usual fashion for obtaining histological material. The procedure will be performed with rapid onsite evaluation. Onsite cytopathologist will evaluate the adequacy and the degree of pathological changes. Based on the information provided by the cytopathologist, the endosonographer will repeat the FNA until enough histological material is obtained to confirm a diagnosis. Adverse effect of procedure will be assessed immediately after procedure and during the first 30 days with a follow-up phone call.

Statistical analysis	For descriptive analyses, continuous variables will be reported as a mean \pm SD or median (interquartile range) and comparison

	
between two groups will be done by Paired t- test. Categorical variables will be reported as frequencies with percentages and compared using chi-square test or Fisher's exact test. Two sided P values less than 0.05 will be considered statistical significance. Descriptive analysis will be performed in terms of DNA yield per sample, ability to complete WES, histology and cytology yield per sample.

Trial duration	Approximately 1 year

List of Abbreviations

This list includes all abbreviations used in the document in alphabetic order. Abbreviated terms are spelled out and the abbreviation is indicated in parentheses at its first appearance in the text section.

CBC	Complete Blood Cell count
EUS	Endoscopic Ultrasound
FNA	Fine Needle Aspiration
FNB	Fine Needle Biopsy
ROSE	Rapid onsite evaluation
GCP	Good Clinical Practice
GI	Gastrointestinal
INV	Investigator
INR	International Normalized Ratio
IRB	Internal Revenue Board
LN	Lymph Node
SNI	Standardized Numerical Identifier

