2. STUDY OBJECTIVES

2.1 Primary Objective:

To compare EUS guide fine needle biopsy versus fine needle aspiration for whole exome sequencing and genomic profiling in tissue sampling of pancreatic solid tumors.

2.2 Secondary Objectives:

- To compare the DNA yield of FNB versus FNA in tissue sampling of pancreas cancer including sufficient DNA to complete un-amplified whole exome sequencing.
- To compare the number of needle passes necessary to obtain adequate tissue sample to make a cytological/histological diagnosis when FNB is used as compared to the conventional FNA for pancreas cancer
- To compare the histology quality of the specimens obtained via FNB as compared to conventional FNA.
- To compare the yield of tissue sufficient for targeted (Foundation Medicine Assay) genomic profiling of pancreas tumors.
- To estimate the safety profile of FNB as compared to conventional FNA. (by historical comparison)
- Per needle adequacy for cytology

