8.2 Study Protocol

- 1) Filling the “Pre-Procedure Patient Registration” section of the “Registration and Data Collection” form
- 2) Review of the signed informed consent before the start of procedure.
- 3) All patients will undergo conscious sedation or Monitored Anesthesia Care (MAC) for the duration of the procedure. Conscious section and/or MAC are the standard method of sedation for all patients that have EUS at our institution, unless contraindicated.
- 4) Morphologic features of the lesion will be examined and documented in the procedure report. Based on the location and type of the lesion, the participating endosonographer determines the necessity of performing an FNA. If FNA deemed necessary, the patient will be included in the study.

- 5) Randomization of needle order. The first needle to be used will be selected by randomization using block randomization in envelopes (FNA first, FNB first) by tumor location (1 block for head tumors, 1 block for body/tail tumors).
- 6) Conventional FNA will be alternated with FNB (22 gauge for all sites) in the usual fashion for obtaining histological material. A minimum of 2 passes (1 with each needle) will be obtained from all lesions. Conventional FNA will be performed with a standard 25g needle (our standard needle) in the usual fashion using back and forth passes for 30 seconds. Negative pressure will be applied for both needle types using the “capillary” technique of withdrawing the stylet slowly (5-10cm per second) during the to and fro movement of the needle. All FNA material will be expressed onto a glass slide. Visible core samples will be removed and placed in formalin after an initial “touch prep” (light touch of tissue to slide). The presence or absence and length (in mm) of grossly visible each core will be recorded by the cytotechnologist/study personnel. Standard passes (alternating with each needle) will be repeated in pairs until an adequate sample is obtained or the endoscopist feels that no further sampling is warranted. Then, a 2nd and 3rd set of passes (one with each needle) will be performed to collect material for biobanking and DNA and RNA extraction. The sample will be expressed into a sealed biospecimen container and flash frozen in liquid nitrogen, then stored at -80C. If no material is obtained, the research pass will be repeated up to a maximum of 2 passes for each needle.

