- 7) After each pass of needle, the on-site cytotechnologist will evaluate the adequacy and the degree of the pathological changes in the obtained material. Based on the information provided by the cytotechnologist, the endosonographer will repeat the FNA until enough material is obtained to confirm the clinical diagnosis. The initial determination of adequacy will be made by the onsite cytotechnologist. The final determination of cytological adequacy will be made by the study pathologist (AN) based on the criteria below.
- 8) Separate sets of slides and formalin jars will be produced in the GI suite from the tissue obtained from each type of the needle. Each pass will be placed on separate slides and

formalin jars with labelling (A, B). 9) In order for the pathologist to remain blinded of the needle type that the tissue was obtained with, two separate slide sets will be generated and each set will be labeled as “*Slide Set A or B*”. Slides that are prepared from the FNB will be labeled as “*Slide Set B*” depending on the parity of the assigned SNI number. Slides that are prepared from the conventional FNA needle will be labeled as “*Slide Set A*” to complete each pair 10) Pathology interpretation for clinical purposes will be done by the on-call pathologist of the day, using all material available. For study purposes a single study pathologist (AN) will interpret all of the slides. The pathologist will evaluate the slides for cell quantity (adequate vs. scanty/acellular), grade of dysplasia (atypical vs. malignant cells), and presence of core samples.

11) Each slide set (A or B) will be evaluated and reported separately for research purposes and accumulatively to generate the patient’s pathology report for medical records.

12) Quarterly, the available data will be reviewed retrospectively and the rate of anticipated complications will be calculated. Anticipated complications of EUS with FNA include, but are not limited to post-procedure pancreatitis, bleeding, perforation, and infection. Serious adverse events from FNA are rare but include life threatening events, inpatient hospitalization, prolongation of existing hospitalization or any unanticipated complication including death as a result of the procedure will be reported to Mayo Clinic IRB.

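### The number-of-passes comparison has no per-needle definition, and its natural source is an on-site adequacy call for which no masking is described

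*Combined protocol and SAP*

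**What the plan says.** - **Objective.** Section 2.2 lists, among six secondary objectives: "To compare the number of needle passes necessary to obtain adequate tissue sample to make a cytological/histological diagnosis when FNB is used", compared with conventional FNA. Neither 2.2 nor 9.1 says whose adequacy reading counts or how passes are credited to a needle.
- **On-site call.** Section 8.2 item 7: "After each pass of needle, the on-site cytotechnologist will evaluate the adequacy and the degree of the pathological changes in the obtained material". It continues: "Based on the information provided by the cytotechnologist, the endosonographer will repeat the FNA until enough material is obtained to confirm the clinical diagnosis". The Protocol Synopsis (Study design) gives the task to a different role: "Onsite cytopathologist will evaluate the adequacy and the degree of pathological changes".
- **Stopping.** Section 8.2 item 6: "Standard passes (alternating with each needle) will be repeated in pairs until an adequate sample is obtained or the endoscopist feels that no further sampling" (quote cut short; the endoscopist's own judgement is the second way to stop). Section 8.1 also lets the endoscopist switch needles if two passes have not given an adequate sample.
- **Two readings.** Item 7: "The initial determination of adequacy will be made by the onsite cytotechnologist". It assigns the final cytological determination to the study pathologist.
- **Masking.** Item 9 opens: "In order for the pathologist to remain blinded of the needle type", and describes slide sets A and B. It assigns FNB to Set B by reference to the parity of the patient identifier, and FNA to Set A. No other masking step is described, although the synopsis calls the trial single blinded.
- **Separate material.** Item 8 puts each pass on its own slides and in its own jar.

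**The concern.** Adequacy is a judgement, and the stated hypothesis is that FNB does better. The on-site reader works in the room while the needles alternate, and item 6 has the cytotechnologist or study personnel record whether a core is visible and how long it is. If that reader accepts borderline FNB material more readily than borderline FNA material, a count built on those calls is shorter for FNB even when the needles are equal. The endoscopist handles the needle and can also end sampling or change needle, so masking the on-site reader alone would not close the gap. A masked reading exists, but nothing links it to the pass count. At stake is one secondary comparison, with any error most likely in the direction of the hypothesis.

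**Working it through.** **1. The plan's own figure.** Section 9.1 claims at least 80% power for McNemar's test with 50 pairs at the two-sided 5% level. The exact test, averaged over the binomial number of discordant pairs, gives 81.2% (25% difference, 38% discordant) and 80.8% (20% difference, 25% discordant). The claim reproduces. It concerns DNA adequacy and does not depend on the on-site call. The documents give no figure for the pass count.

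**2. Raw count.** Item 6 makes diagnostic passes in pairs, one with each needle. (Item 7 speaks only of repeating the FNA; I read that as sampling in general.) While pairs are completed, the FNA minus FNB difference in passes made is 0 in every patient, whatever the reader says.

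**3. Derived count.** Assume sampling stops after the first pair in which either needle is called adequate, with at most 4 pairs (the cap is assumed). Score each needle by its first adequate pass, or one more than the last pass made if it had none. Let *a* and *b* be the chances per pass that an FNA and an FNB pass are called adequate, and q = (1−a)(1−b). The difference FNA minus FNB is then +1, −1 or 0:

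- P(+1) = b(1−a)(1−q⁴)/(1−q)
- P(−1) = a(1−b)(1−q⁴)/(1−q)
- mean = (b−a)(1−q⁴)/(1−q)

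**4. Assumed inputs.** The needles are identical. Per pass, 50% are clearly adequate and 20% or 30% are borderline. The call probability is the clear share plus borderline share × acceptance. Example: 20% borderline, accepted 60% for FNB and 40% for FNA. Then b = 0.50 + 0.20×0.60 = 0.62, a = 0.50 + 0.20×0.40 = 0.58, q = 0.38×0.42 = 0.1596, and the mean is 0.04×0.9994/0.8404 = 0.048 passes.

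**5. Results.** N = 50, the plan's paired t-test at two-sided 0.05, exact over the three-outcome distribution:

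| Borderline | Acceptance FNB/FNA | b | a | False difference (passes) | Chance of significance favouring FNB |
|---|---|---|---|---|---|
| 20% | 50/50 | 0.60 | 0.60 | 0 | 2.6% |
| 30% | 50/50 | 0.65 | 0.65 | 0 | 2.7% |
| 20% | 60/40 | 0.62 | 0.58 | 0.048 | 6.7% |
| 30% | 60/40 | 0.68 | 0.62 | 0.068 | 10.2% |
| 20% | 70/30 | 0.64 | 0.56 | 0.095 | 14.5% |
| 30% | 70/30 | 0.71 | 0.59 | 0.136 | 27.3% |

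With 70% clear and 10% borderline at 60/40 (b = 0.76, a = 0.74), the chance is about 4%.

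**6. A second bias model.** Suppose instead that a truly inadequate FNB pass is called adequate with probability u. Under the same stopping rule, the total false-positive rate is about 5% at u = 0. Across true adequacy from 80% down to 50%, it is 6–9% at u = 0.1, 8–20% at u = 0.2 and 12–39% at u = 0.3. Nearly all of the excess favours FNB.

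**7. Truncation.** The share of patients in whom at least one needle has no pass called adequate is P(+1) + P(−1) + q⁴. In the table's scenarios this is 52–57%. Any passes-to-adequate count, masked or not, therefore needs a rule for such needles.

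**The case against.** The strongest reply is that passes are paired, so the on-site call cannot give one needle fewer passes. That is right for the raw count, and a reader who infers that the call itself shortens FNB sampling goes further than item 6 allows. Pairing does not protect a derived count. If each needle is instead run separately to its own first adequate call, which is not the documented procedure, the same assumptions give a false difference of 0.09–0.25 passes. Pairing roughly halves that and leaves the chance of a false positive similar.

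It can also be said that the plan never states that the endpoint uses the on-site call, and that item 7 reserves the final determination for a pathologist who is meant to be masked. That stands: the provable gap is the missing definition, and a masked definition is equally open. Lack of masking on site is likewise inferred from silence and from the on-site duties; no section says the reader knows the needle.

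A reader might further infer that the study pathologist could be the on-site or on-call reader, so that bias reaches the cytology and histology aims. The documents do not support this. Section 8.2 names an on-site cytotechnologist, an on-call pathologist for clinical reads and a single study pathologist. That nothing bars overlap is a gap, not evidence of it.

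Finally, the pass count is one of six secondary objectives, is absent from the five Specific Aims and is not named in 9.1. This limits the consequence.

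**Conclusion.** The point holds for one secondary comparison. The number of passes needed has no per-needle definition. Its natural source is an on-site call with no described masking, and sampling can also be ended or altered by the endoscopist, who knows the needle. Differential leniency could then produce a false difference favouring FNB: 0.05 to 0.14 passes, with about a 7% to 27% chance of significance, in the 60/40 and 70/30 scenarios. Those figures illustrate a mechanism. The clear and borderline shares, the leniency, the 4-pair cap and the scoring rule are all assumed, and milder inputs give about 4%. They should not be read as an estimate of bias in this trial. The 1.1 ug DNA adequacy endpoint and the power statement are not affected.

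**What to change.** 1. **Define the comparison in 2.2 and 9.1** from the study pathologist's masked reading of each pass, using item 8's separate slides and jars.
   - Make the main comparison masked adequacy of the first pass with each needle, paired, by McNemar's test. Item 6 requires at least one pass with each needle from every lesion, so this does not depend on when sampling stopped.
   - Report passes to first masked-adequate pass as supporting, with a stated rule for a needle with none, for example censoring at its last pass made.
   - Leave the on-site call to its clinical role and report its agreement with the masked call by needle.
2. **Correct item 9** so that the A/B label varies by patient, as the parity wording implies. As written, FNB is always Set B, and a fixed code undermines the masking that step 1 relies on.
3. **Reconcile the on-site reader's role** (cytopathologist in the synopsis, cytotechnologist in 8.2), and state that the study pathologist does not read on site or on call for trial patients.

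The cost is protocol wording, some pass-level reading time for the same pathologist and a small rota restriction. No extra pass, patient or reader is needed.

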1.0 INTRODUCTION

1.1 Background

Pancreas cancer is a highly fatal disease with a 5 year overall survival is of only 8%¹. The shorter survival and the poor outcome may be due to late stage presentation, tendency toward early metastases and aggressive biologic behavior of pancreas cancer with diverse genetic alterations that drive the tumor to early dissemination. Endoscopic ultrasound (EUS) has been established as a one of the valuable tools for evaluation of pancreatico-biliary disease. EUS-guided FNA is important for cytological and pathological evaluation of pancreatic cancer. It is minimally invasive, rapid and accurate for staging and diagnosis of pancreas cancer. The overall sensitivity of EUS-FNA is 85% (95% CI, 0.84-.86) and specificity of 98% (95% CI, 0.97-0.99)² for pancreatic tumor diagnosis. Over the past 20 years there have been significant developments done in the field of needle technology and sampling techniques to obtain the good quality of cytologic materials. However, over time it has been obvious that size of needle, use of stylet and suction techniques has small value in increasing the diagnostic yield of pancreas cancer³⁻⁵.

There has been recent advancement in the field of FNB design including needle tip and use of more flexible shaft. However, multiple randomized trials and metaanalysis have failed to show the superiority of FNB vs FNA for pancreatic lesions^{6,7}. Therefore difficulties still persist to diagnose pancreas cancer at early stage. The development of pancreas cancer is a multistep process that involves wide range of genetic alteration. However, the paradigm shift for early diagnosis of pancreas cancer has changed over recent years. Now a day multiple gene mutation and expression profiling of pancreas cancer has become a research priority. A number of efforts have been made for molecular diagnosis of pancreas cancer at early stage that would facilitate to design a specific chemotherapy preoperatively.

EUS- guided FNA is not only important for histopathologic characterization of pancreas lesion but has also opened the door for genomic analysis of pancreas cancer tissue. Several techniques

have been investigated for improving the pancreatic cancer diagnosis, mainly in on the genetic analyses⁸⁻¹⁰. Studies have demonstrated that the feasibility of genomic profiling, next generation sequencing and performing the multiple genetic tests from a small sample of pancreas tumor tissue obtained by endoscopic-ultrasound guided fine needle aspiration¹¹.

With the advances in the needle technology to increase the yield of core tissue in addition to cytology, a new needle has been developed termed “Shark Core needle”. The needle has a sharpened point in the shape of a fork-tip that promotes the collection of core sample by shearing a material from the target lesion during to-and fro-movement of the needle. Recently published studies have demonstrated its benefit in acquiring adequate core tissue compared to conventional FNA needle^{12,13} for pathological evaluation. With this advancement, it will be possible to obtain more DNA from the tumor tissue and carry out comprehensive whole exome sequencing of pancreas cancer. The contribution will be significant because a large amount of DNA will facilitate to carry out genomic profiling and chemo sensitivity test of pancreas cancer preoperatively. This will be a significant breakthrough in the field of precision medicine. Though several studies have been conducted to characterize the expression profiles of pancreas cancer¹⁴ using FNA specimens, the ability to characterize the global genetic mutational status from FNB specimens has not been proven yet. It has been understood that the low quantity of cells, obtained from the FNA specimens preclude the precise determination of a tumors genetic status¹⁵. None of the studies have reported the comparison between FNB needle “Shark Core” and Standard FNA needle for genomic profiling of pancreas cancer. Thus, to facilitate a development of personalized cancer treatment we sought to determine whether the new FNB needle “Shark Core” would be capable of performing widespread whole exome sequencing of pancreas tissue from FNB specimens. Therefore the main of this study is to compare the DNA yield and genomic profiling of pancreas cancer between FNB needle and standard FNA needle.

1.2 Rationale for performing the study

Based on the above facts, there is still a need of prospective randomized trial to evaluate the efficacy of FNB in conducting the comprehensive whole exome sequencing of pancreas cancer. . We designed the trial to compare of FNB versus FNA for whole exome sequencing and genomic profiling of pancreas cancer. The rationale for choosing the 25g as the standard comparator is based on the recent systematic review of needle devices by Wani et al. which concluded “*The use of a 25-gauge needle is associated with a higher diagnostic yield compared with a 22-gauge needle in patients undergoing EUS-FNA of pancreatic masses.*”¹⁶.

